5.5.8.2. Gated Secondary

For the gated secondary of the estimated mean proportion of patients with a 50% or greater reduction from baseline in the weekly frequency of cluster headache attacks during the 12-week double-blind treatment phase, a categorical, pseudo-likelihood-based repeated measures analysis will be used. The endpoint for comparing GMB300mg with placebo will be estimated as the main effect of treatment from the categorical MMRM analysis across Weeks 1-12. This analysis will be implemented using the GLIMMIX procedure in SAS® to compare treatments and include the fixed, categorical effects of treatment, gender, verapamil use, visit/week, and treatment-by-visit/week interaction, as well as the continuous, fixed covariate of baseline value. An unstructured covariance structure will be used to model the within-patient errors (denoted by TYPE=CHOL in the RANDOM statement). The Newton-Raphson method with ridging will be used for nonlinear optimization (denoted by including NLOPTIONS TECH=NRRIDG). The Kenward-Roger approximation will be used to estimate denominator degrees of freedom. If the model does not converge, the Fisher's scoring algorithm will be utilized by the SCORING option in SAS®. If the model still fails to converge, the model will be fit using covariance matrices in the following order specified by a decreasing number of covariance parameters until convergence is met: heterogeneous Toeplitz, heterogeneous autoregressive, Toeplitz, and

autoregressive. If necessary, both fitting algorithms will be used in the pre-specified order before proceeding to the next covariance structure in the sequence. For models where the unstructured covariance matrix is not utilized, the sandwich estimator (Diggle et al. 1994) will be used to estimate the standard errors of the fixed effects parameters. The sandwich estimator is utilized by the EMPIRICAL option in SAS®. When the sandwich estimator is utilized, the Kenward-Roger approximation for denominator degrees of freedom cannot be used. Instead, the denominator degrees of freedom will be partitioned into between-subject and within-subject portions by the DDFM=BETWITHIN option in SAS®.

For the final gated secondary outcome, sustained response is defined as the proportion of patients with a reduction from baseline of 50% or greater in the weekly cluster attack frequency beginning at Weeks 3/4 and maintained at Weeks 5/6, 7/8, 9/10, and 11/12. A non-responder imputation for missing values will be used. Specifically, all patients who discontinue study treatment at any time prior to Weeks 11/12, for any reason, will not be considered a sustained responder.

Treatment differences in the proportions of patients meeting sustained response definition will be determined using Koch's Nonparametric Randomization-Based Analysis of Covariance method (Koch et al. 1998). This method will adjust for pooled investigative site by including it as a stratification variable, and will also adjust for the continuous baseline value, gender, and verapamil use. A SAS®/IML macro (NParCov3) (Zink and Koch 2012) will be used for the calculation. The options with this SAS®/IML macro are specified in the example SAS® code below.

```
%NPARCOV3(outcomes =[response],  
covars = [baseline] [gender] [verapamil use],  
trtgrps = [treatment],  
strata = [PINVID],  
hypothesis = NULL,  
transform = NONE,  
combine = FIRST,  
c = 1,  
dsnin = [input],  
dsnout = [output]);
```

In this method, the option of "hypothesis=NULL" indicates that the variance covariance structure will be calculated under the assumption that the means and covariance matrices of the treatment groups are equal and therefore computes a single covariance matrix for each stratum. The option of "combine=FIRST" indicates that the covariate adjustment will be performed after a weighted average of treatment group differences across pooled investigative sites to account for the

possibility of small numbers of patients at some sites. The option of “c=1” indicates the use of Mantel-Haenszel weights for each pooled investigative site. The option of “transform=NONE” indicates that there is not a transformation of the data.

If the sample size is increased, the CHW test statistic will be calculated for the gated secondary endpoints. The analysis results of the secondary gatekeeper objectives will be evaluated if the placebo versus GMB300mg comparison is significant for the primary efficacy analysis at a one sided $\alpha=0.025$ significance level using the methodology described in [Appendix 1](#). No analysis result will be considered to be statistically significant after multiplicity adjustment unless all of the secondary gatekeeper objectives preceding it are found to be statistically significant.

5.5.8.3. Additional Secondary Efficacy Analyses

[Table CGAM.5.4](#) summarized all the planned additional secondary efficacy analyses for SP III, SP III and first week of SP IV combined, and SP IV.

For the continuous additional secondary and exploratory efficacy measures, the change from baseline to each postbaseline period will be estimated for each treatment from repeated measures analyses as described in [Section 5.5.8.1](#). The treatment comparison at each biweekly interval and overall across 12 weeks will be provided. As discussed in [Section 5.5.1.1](#), for the efficacy measures that are not derived from cluster headache attack frequency, the baseline average daily cluster headache attack frequency category (≤ 4 vs. >4) will be added as a covariate in the MMRM model.

For the categorical additional secondary and exploratory efficacy measures including 30%, 50%, 75% and 100% response, the percentage of patients meeting response criteria at each period will be estimated for each treatment from the categorical, pseudo-likelihood-based repeated measures analysis of visitwise binary outcomes indicating whether patients meet response criteria. This analysis will be implemented using the GLIMMIX procedure in SAS® as described in [Section 5.5.8.2](#). The treatment comparison at each biweekly interval and overall across 12 weeks will be provided. As discussed in [Section 5.5.1.1](#), for the efficacy measures that are not derived from cluster headache attack frequency, the baseline average daily cluster headache attack frequency category (≤ 4 vs. >4) will be added as a covariate in the GLIMMIX model.

Table CGAM.5.4. Other Secondary and Exploratory Efficacy Variables and Their Derivation

Study Phase (SP) III	SP III and First Month of SP IV Combined	SP IV	Efficacy Variable	Analyses
Change from baseline to each 14-day interval (Weeks 1/2, 3/4, 5/6, 7/8, 9/10, 11/12)	Change from baseline to each 14-day interval (Weeks 1/2, 3/4, 5/6, 7/8, 9/10, 11/12, 13/14, 15/16)	No planned analyses	1. Weekly cluster headache attack frequency	Variables will be analyzed by a repeated measures analysis using a model as described in Section 5.5.8.1.
Change from baseline to each 14-day interval (Weeks 1/2, 3/4, 5/6, 7/8, 9/10, 11/12)	No planned analyses	No planned analyses	1. Weekly average cluster headache attack pain severity in the remaining cluster headache attack days; 2. Weekly total cluster headache attack duration; 3. Weekly number of times using oxygen; 4. Weekly number of times using oral Triptan, sumatriptan nasal spray or zolmitriptan nasal spray; 5. Weekly number of times using sumatriptan Sc; 6. Weekly number of times using acetaminophen/paracetamol or NSAIDs; 7. Number of times using oxygen per cluster headache attack; 8. Number of times using oral triptan, sumatriptan nasal spray or zolmitriptan nasal spray per cluster headache attack; 9. Number of times using sumatriptan Sc per cluster headache attack; 10. Number of times using acetaminophen/paracetamol or NSAIDs per cluster headache attack; 11. Total weekly dose of oral triptan, sumatriptan nasal spray and zolmitriptan nasal spray combined; 12. Total weekly dose of sumatriptan subcutaneous; 13. Total weekly dose of oral triptan; 14. Total weekly dose of sumatriptan nasal spray; 15. Total weekly dose of zolmitriptan nasal spray.	Variables will be analyzed by a repeated measures analysis using a model as described in Section 5.5.8.1-5.5.8.3

Other Secondary and Exploratory Efficacy Variables and Their Derivation

Study Phase (SP) III	SP III and First Month of SP IV Combined	SP IV	Efficacy Variable	Analyses
Value at each visit (Visits 6, 8, 9, corresponding to Months 1, 2, 3)	No planned analyses	Value at each visit (Visits 16, 22, corresponding to Months 9 and 15)	1. Patient Global Impression of Improvement (PGI-I) Score	Variables will be analyzed by a repeated measures analysis using a model as described in Section 5.5.8.3 but without baseline covariate
Categorical variables at each 14 day-interval (Weeks 1/2, 3/4, 5/6, 7/8, 9/10, 11/12)	Categorical variables at each 14 day-interval (Weeks 1/2, 3/4, 5/6, 7/8, 9/10, 11/12, 13/14, 15/16)	No planned analyses	1. 30% Response 2. 50% Response 3. 75% Response 4. 100% Response 5. 30% reduction in weekly total cluster headache attack duration	For all variables, the visitwise percentages of patients meeting criteria will be compared between treatments using a categorical, repeated measures analysis described in this Section 5.5.8.3.
Categorical variables at each visit (Visits 6, 8, 9, corresponding to Months 1, 2, 3)	No planned analyses	Categorical variables at each visit (Visits 16, 22, corresponding to Months 9 and 15)	1. Proportion of patients reporting a score of 1 ("very much improved") or 2 ("much improved") on Patient Global Impression of Improvement (PGI-I)	For all variables, the visitwise percentages of patients meeting criteria will be compared between treatments using a categorical, repeated measures analysis described in this Section 5.5.8.3 but without baseline value covariate

Abbreviations: NSAIDs = nonsteroidal anti-inflammatory drugs; SP = study phase.

5.5.9. Safety Analyses

The safety analyses will be conducted on the safety population during the double-blind treatment phase (SP III), and on the GMB-treated population during the GMB-treated time (SP III/IV combined) and the GMB-treated time plus post-treatment time (SP III/IV/V combined). All the safety analyses outlined below will be conducted as long as the safety measures were collected at the specific study phase.

The safety and tolerability of treatment will be assessed by summarizing the following:

- adverse events
 - treatment-emergent adverse events
 - by PT
 - by PT nested within SOC
 - by maximum severity
 - serious adverse events by PT nested within SOC
 - adverse events leading to discontinuation by PT nested within SOC
 - adverse events of special interest
- suicide-related thoughts and behaviors by C-SSRS
- vital signs and weight
- laboratory measurements
- electrocardiograms
- antibodies (ADA and NAb)

The baseline and postbaseline for all safety measures are described in [Table CGAM.5.3](#) unless specified otherwise. For SAEs, only events with a start date during the post-baseline phase will be accounted for the corresponding study phase analysis.

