5.1. Study Design

Study CGAM is a Phase 3 multi-center, outpatient, randomized, double-blind, placebo-controlled study of galcanezumab 300 mg for the prevention of chronic cluster headache. The study has 5 study phases (SP):

- SP I (screening/washout phase)
- SP II (pre-randomization diary phase)
- SP III (double-blind treatment phase)
- SP IV (optional open-label extension phase)
- SP V (post-treatment follow-up phase)

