SP III/IV/V Combined (GMB-treated time + post treatment time)		2) patients who received placebo during SP III and entered the open-label phase with at least one galcanezumab injection.	

Abbreviations: ePRO = electronic patient reported outcome; GMB = galcanezumab; SP = study phase.

a Analyses in SP III and first 4 weeks of SP IV combined, will be conducted for ePRO data only.

Treatment effects will be evaluated based on a 2-sided significance level of 0.05 for all the other efficacy and safety analyses. Ninety-five percent (95%) CI for the difference in least-square means (LSMeans) between treatment groups will be presented. Adjustments for multiple comparisons for the analyses corresponding to the primary and gated secondary objectives are described in the sections on the primary and secondary efficacy analyses below. There will be no adjustments for multiplicity for analyses of other data.

A repeated measures analysis refers to a restricted maximum likelihood (REML)-based, mixed-effects repeated measures (MMRM) analysis using all the longitudinal observations at each postbaseline visit/week.

Categorical comparisons between treatment groups for safety measures will be performed using Fisher's exact tests, where appropriate.

Any change to the data analysis methods described in the protocol will require an amendment ONLY if it changes a principal feature of the protocol. Any other change to the data analysis methods described in the protocol, and the justification for making the changes, will be described in the SAP and/or in the clinical study report.

Additional exploratory analyses of the data will be conducted as deemed appropriate.

Statistical analysis of this study will be the responsibility of Eli Lilly and Company (Lilly) or designee. SAS®software will be used to perform most or all statistical analyses.

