Treatment-emergent changes in vital signs and weight, ECG parameters	Patients in GMB-treated population with a baseline and at least one postbaseline observation	
For patients treated with GMB during SP III: Last non-missing value from Visits 1-3 for BP, pulse and ECG;
 
All Visits 1-3 for weight and temperature;
 
For patients treated with placebo during SP III: Last non-missing value from Visits 1-9 for BP, pulse and ECG;
 
All Visits 1-9 for weight and temperature.
	All visits after first dosing of GMB up to Visit 22: Visits 3.01-22 for GMB-treated patients during SP III; Visits 9.01-22 for placebo treated patients during SP III.
Treatment-emergent immunogenicity	Patients in GMB-treated population who are evaluable for TE ADA	Visit 3	All visits after first dosing of GMB up to Visit 22: All Visits 3.01-22 for GMB-treated patients during SP III; All Visits 9.01-22 for placebo treated patients during SP III.

Patient Population with Baseline and Postbaseline Definitions by Study Phase and Type of Analysis

Study Phase / Analysis	Patient Population	Baseline Observation	Postbaseline Observation(s)
Study Phase IV (Open-label Extension Phase)			
Efficacy analyses (PGI-I)	Open-label population		V16 and V22
Study Phase III, IV and V			
TEAEs	GMB-treated population	Visits 1-3 before double-blind phase dosing for patients treated with GMB during SP III; Visits 1-9 before open-label phase dosing for patients treated with placebo during SP III.	All visits on or after first dosing of GMB up to Visit 24: Visit 3 after dosing– Visit 24 for GMB-treated patients during SP III; Visit 9 after dosing to Visit 24 for placebo treated patients during SP III.
SAEs, Discontinuations due to AEs	GMB-treated population	NA	All visits on or after first dosing of GMB up to Visit 24: Visit 3 after dosing to Visit 24 for GMB-treated patients during SP III; Visit 9 after dosing to Visit 24 for placebo treated patients during SP III.

Patient Population with Baseline and Postbaseline Definitions by Study Phase and Type of Analysis

Study Phase / Analysis	Patient Population	Baseline Observation	Postbaseline Observation(s)

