5.5.5.1. Duration of Exposure

From the dose information recorded on the eCRF, the following duration of exposures will be derived and summarized:

- duration of exposure in days during SP III calculated as Treatment end date (disposition date in SP III) – First date IP administered during SPIII + 1

- duration of exposure in days during SP IV calculated as Treatment end date (disposition date in SP IV) – First date IP administered during SP IV + 1
- duration of exposure in days during SPIII/SP IV for the GMB-treated population calculated as GMB treatment end date (last disposition date in SP III/IV) – First date GMB administered during SP III/IV + 1

Comparisons between treatment groups will be performed for SP III using an ANOVA with treatment and pooled investigative site in the model.

The number of full doses will also be summarized.

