5.5.9.1.1. Adverse Events

Treatment-emergent AEs are defined as the reported AEs that first occurred or worsened during the post-baseline phase compared with baseline phase. For events occurring on the day of first administration of study drug and on the day of first open-label treatment when applicable, the CRF-collected flag will be used to determine whether the event was pre-treatment versus post-

treatment. For each TEAE, the severity level of the event (mild, moderate, or severe) will be determined by patient or physician opinion. The Medical Dictionary for Regulatory Activities (MedDRA) Lowest Level Term (LLT) will be used in the treatment-emergent computation. For each LLT, the maximum severity at baseline will be used as the baseline severity. If the maximum severity during post-baseline is greater than the maximum baseline severity, the event is considered to be treatment-emergent for the specific post-baseline period. For events with a missing severity during the baseline period, it will be treated as “mild” in severity; for events with a missing severity during the postbaseline period it will be treated as “severe” for TEAE computation. For each patient and TEAE, the maximum severity for the MedDRA level being displayed (PT, High-Level Term [HLT], or SOC) is the maximum postbaseline severity observed from all associated LLTs mapping to that MedDRA level.

For events that are gender-specific, the denominator and computation of the percentage will include only patients from the given gender.

5.5.9.1.1.1. Potential Hypersensitivity Events

Potential hypersensitivity events will be defined using the following terms (standard MedDRA query [SMQ]):

- broad and narrow terms in the Anaphylactic reaction SMQ (20000021)
- broad and narrow terms in the Angioedema SMQ (20000024)
- broad and narrow terms in the Hypersensitivity SMQ (20000214)

A listing of patients having an event identified from these analyses will be medically reviewed to determine if the terms identified represent events likely hypersensitivity in nature. Listings should include information on timing of event relative to latest dose of study drug administration, the event term from this query, other AEs for the patient and timing, any abnormal laboratory findings, concomitant medication, medical history and pre-existing conditions. Only those that are judged medically to be events likely hypersensitivity in nature will be included in the final tables.

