The number and percentage of patients with potential and/or likely TEAEs will be summarized by treatment groups using MedDRA PT nested within the SMQ. Events will be ordered by decreasing frequency within the SMQ. The number and percentage of patients with likely hypersensitivity SAEs and AEs resulting in study drug discontinuation will be presented by treatment groups using MedDRA PT, and ordered by decreasing frequency of PT.

The number and percentage of patients with likely hypersensitivity TEAEs by maximum severity will be summarized by treatment groups using MedDRA PT.

The number and percentage of patients with likely hypersensitivity TEAEs by timing will be summarized using MedDRA PT. Events will be ordered by decreasing frequency of PT. Note the timing of the hypersensitivity events is collected through eCRF and categorized into the following four categories:

- immediate - occurs within minutes (<60 minutes) from study drug administration
- acute reaction - occurs from 1 up to 6 hours from study drug administration
- delayed reaction - occurs from >6 hours through 14 days from study drug administration, which will be split into 2 categories: on the same day of injection and after the day of injection
- reaction >14 days

5.5.9.1.1.2. Adverse Events Related to Injection Sites

Adverse events related to injection sites will be defined using terms from the MedDRA HLT Injection site reactions.

The number and percentage of patients with TEAEs related to injection sites, SAEs related to injection sites, and AEs related to injection sites resulting in study drug discontinuation will be summarized using MedDRA PT. Events will be ordered by decreasing frequency of PT term.

The number and percentage of patients with TEAEs related to injection sites by maximum severity will be summarized by treatment groups using MedDRA PT. For each patient and injection site related event, the maximum severity for the MedDRA level being displayed (PT) is the maximum post-baseline severity observed from all associated LLTs mapping to that MedDRA level.

The number and percentage of patients with TEAEs related to injection sites by timing will be summarized using MedDRA PTs ordered by decreasing frequency. Note the timing of AEs related to injection sites is collected through eCRF and categorized into the same categories as for hypersensitivity events.

5.5.9.1.1.3. Upper Respiratory Tract Infections

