Upper respiratory tract infections will be defined using all the PTs from the 2 HLTs of “Upper respiratory tract infections” and “Upper respiratory tract infections NEC” as defined in MedDRA.

The number and percentage of patients with TEAEs of upper respiratory tract infections will be summarized by treatment group using MedDRA PTs. Events will be ordered by decreasing frequency in the GMB group.

The number and percentage of patients with TEAEs of upper respiratory tract infections by maximum severity will be summarized by treatment group using MedDRA PTs. For each patient and upper respiratory tract infection event, the maximum severity for the MedDRA level being displayed (PT) is the maximum post-baseline severity observed from all associated LLTs mapping to that MedDRA level.

By-subject listings of treatment-emergent upper respiratory tract infections, and upper respiratory tract infections leading to study drug discontinuation will be provided.

5.5.9.1.2. *Suicide-Related Thoughts and Behaviors*

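### The pooled galcanezumab adverse-event tables plan percentages of patients without time at risk; adding patient-years and follow-up through SP V would be a cheap improvement

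*SAP*

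**What the plan says.** Table CGAM.5.2 (SAP 5.5.1) puts everyone exposed to galcanezumab into one GMB300mg column. Besides patients given galcanezumab in SP III, it takes in "patients who received placebo during SP III and entered the open-label phase with at least one galcanezumab injection". Safety is then summarised "on the GMB-treated population during the GMB-treated time (SP III/IV combined) and the GMB-treated time plus post-treatment time (SP III/IV/V combined").

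The event format is a count and percentage of patients. SAP 5.5.9.1.1.3 states "The number and percentage of patients with TEAEs of upper respiratory tract infections will be summarized by treatment group using MedDRA PTs", and 5.5.9.1.1.1 states "The number and percentage of patients with likely hypersensitivity SAEs and AEs resulting in study drug discontinuation will be presented by treatment groups". The injection-site section (5.5.9.1.1.2) uses the same format. For TEAEs in general, SAEs and discontinuations, 5.5.9 says only that they are summarised. The percentage format is inferred from 5.5.9.1.1, where for gender-specific events "the denominator and computation of the percentage will include only patients from the given gender".

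The event window in Table CGAM.5.3 opens at first galcanezumab dose. For the longest analysis it is "Visit 9 after dosing to Visit 24 for placebo treated patients during SP III", and Visit 3 to Visit 24 for those given galcanezumab from the start. SP IV is optional (SAP 5.1).

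SAP 5.5.5.1 summarises "duration of exposure in days during SPIII/SP IV for the GMB-treated population calculated as GMB treatment end date". It plans no duration that includes SP V. SAP 5.5.2 tabulates completion and discontinuation in SP V, overall and by visit, for ITT patients. The registry output in 5.9 gives numbers at risk, patients with an event and event counts, but no time. No patient-year rate or cumulative incidence is planned for any adverse event.

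**The concern.** When follow-up differs this much within one column, the percentage with an event reflects both how often events occur and how long patients were watched. The revision history (Version 4) says the phases were pooled because overall estimates across phases were judged more useful medically than estimates by phase. Such estimates are easier to use with the time at risk beside them.

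Two readings are at stake. One sets the pooled percentages against SP III to ask whether risk changes with longer treatment. The other asks whether events continue after the drug is stopped, which SP V is there to observe. At the second interim analysis all the tables are run while some patients are still in SP IV and SP V (SAP 5.8.1.2), so follow-up will be more uneven still at that point.

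**Working it through.** **1. Length of follow-up.** The Protocol synopsis gives 64 weeks of treatment plus up to 16 weeks of follow-up.
- 12 + 52 = 64 weeks. Visit 22 is at Day 450 (Protocol Attachment 1), and 450/7 = 64.3 weeks, or 15 thirty-day months.
- 64 + 16 = 80 weeks. Visit 24 is at Day 570, and 570/7 = 81.4 weeks, or 19 months. The plan's figures are reproduced to within rounding of the visit schedule.
- Patients who start on placebo get their first galcanezumab at Visit 9 (Day 90): (450 − 90)/30 = 12 months, or (570 − 90)/30 = 16 with SP V.
- A patient on galcanezumab in SP III who declines SP IV contributes about 3 months of SP III/IV time.

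**2. Effect on a percentage.** The documents give no event rates, so all rates here are assumptions. With a constant rate r, the expected share with an event is 1 − exp(−r × days/365.25). At r = 0.20 per year this is 1.6% at 30 days, 17.9% at 360, 21.8% at 450 and 26.8% at 570.

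**3. SP III/IV: rate from the planned summaries.** Take equal halves at 15 and 12 months, with full SP IV uptake and no dropout. Mean exposure is (15 + 12)/2/12 = 1.125 years. The expected percentage is the average of 1 − exp(−r·t/12) over t = 15 and 12. Dividing it by 1.125 gives the rate a reader would compute. For SP III, t = 3 and the divisor is 0.25.

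| True rate per 100 PY | SP III/IV: % | ÷ 1.125 | Shortfall from true | SP III: % | ÷ 0.25 |
|---|---|---|---|---|---|
| 5 | 5.5 | 4.9 | 2.8% | 1.2 | 5.0 |
| 10 | 10.6 | 9.4 | 5.5% | 2.5 | 9.9 |
| 20 | 20.1 | 17.9 | 10.6% | 4.9 | 19.5 |
| 60 | 48.9 | 43.5 | 27.5% | 13.9 | 55.7 |
| 100 | 67.3 | 59.8 | 40.2% | 22.1 | 88.5 |

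At 60 and 100 the pooled figure is 22% and 32% below the SP III figure, although the underlying rate is the same. With 80% uptake, 3% monthly dropout, or both, the pooled figure at 20 stays between 17.9 and 18.1, so the result does not hinge on full uptake.

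**4. SP III/IV/V: reconstruction from disposition.** Suppose the table reports 20% and SP IV uptake is full. SP V completers have t = 19 or 16 months. The others have 15 + s or 12 + s, with s between 0 (leave at once) and 2 (leave at Visit 23). Solving mean[1 − exp(−r·t/12)] = 0.20 for r:
- 80% complete SP V: 15.7 to 16.1 per 100 PY.
- 60% complete SP V: 16.1 to 16.9 per 100 PY.

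This is fairly tight for the galcanezumab-first arm. It is looser for the placebo-first arm, because the ITT disposition table also counts patients who never entered SP IV and so do not belong in the pooled column.

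**5. Limits of a rate.** At r = 0.20 with 162 patients and full uptake, exact Poisson 95% intervals are:
- SP III/IV: 33 events in 163 PY, about 14 to 28 per 100 PY.
- SP III/IV/V: 41 events in 204.7 PY, about 14 to 27.
- One SP III arm of 81: 4 events in 19.8 PY, about 6 to 52.

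If 10% of patients have a first event, all in month 1, a single overall rate is 0.10/(0.9·T/12 + 0.1·0.5/12). That is 44, 9 and 7 per 100 PY at T = 3, 15 and 19 months, with no change in the pattern of events.

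**The case against.** The best case for the plan is that little depends on this. The pooled column is a single group with descriptive statistics only (SAP 5.5.9.1), SP IV and SP V output is rerun at final lock, and the randomised SP III comparison is untouched. Exposure is already summarised for exactly this population over SP III/IV, and for uncommon events the derived rate is close. Even at 20 per 100 PY the 10.6% shortfall sits well inside an interval of 14 to 28. The SAP plans no comparison of pooled rates with SP III, and it allows further exploratory analyses. A patient-year rate also brings its own distortion for early events. All of this stands, and it sets the weight of the point. The permission for exploratory analyses, however, commits to nothing. The planned timing tables for injection-site and hypersensitivity events measure the interval from a dose to the event, not time at risk.

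A reader might go further and infer that SP III/IV/V follow-up is unknown beyond 0 to 4 extra months each, so that a reported 20% could mean anything from 15.3 to 19.9 per 100 PY. The documents do not support that. SP V disposition is tabulated by visit and the visits fall at set days (510 and 570, ±8), so the extremes in which nobody or everybody is followed would be visible. Step 4 gives a spread below 1 per 100 PY in each case.

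A reader might also infer that the pooled tables bias a treatment comparison. They contain none.

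**Conclusion.** The point holds as a low-cost improvement to reporting, not as the correction of an error. The pooled tables carry no time at risk, although follow-up from first galcanezumab dose ranges from one dose to 15 or 12 months, and up to 19 or 16 with SP V. For SP III/IV the practical loss is small for uncommon events and material only for common aggregates such as any TEAE. For SP III/IV/V the loss is a missing follow-up summary that can be rebuilt only roughly, least well for patients who start on placebo. These sizes rest on assumed constant event rates, SP IV uptake, dropout and SP V attendance, none of which the documents give. That the general TEAE, SAE and discontinuation tables use percentages is an inference, though a natural one.

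**What to change.** In SAP 5.5.9, keep the percentages. For the GMB-treated population, and for the SP III arms as a rough reference, add:
- total patient-years at risk, including SP V in the SP III/IV/V tables;
- patients with a first event per 100 patient-years with 95% CI, with time stopped at first event, end of period or data cutoff, for TEAEs, SAEs, adverse events leading to discontinuation and upper respiratory tract infections;
- for injection-site and hypersensitivity events, cumulative incidence at fixed times from first galcanezumab dose (for example 3 and 12 months) or rates split at month 3, instead of one overall rate.

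Minimum version: add to 5.5.5.1 a summary of follow-up time from first galcanezumab dose to last SP V contact.

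The cost is SAP wording and a few table columns, built from dates already collected. The rate assumes a roughly constant hazard within each period, so it supplements the percentages. Precision is limited, especially for the SP III reference and for single preferred terms.
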